This timeline was calculated based on average length of stay for our participating hospice agency and also on national level as well as based on the PST recommendations⁸⁶ and previous work on cognitive behavioral interventions in hospice.ⁱⁱⁱ However, this was only a guideline, and the actual timing and scheduling was tailored to the individual caregiver needs and challenges (the visits were scheduled and confirmed based on the caregiver’s feedback and preferences and with the recognition that unexpected and stressful events can lead to frequent rescheduling). Each intervention visit lasted approximately 45 minutes.

The agenda for the first face to face visit for caregivers (suggested timeline 5-7 days after hospice admission) includes an explanation of the purpose of the visit/call, and confirmation of the three specific problems that the caregiver had selected from the concern list during the consent visit. Caregivers’ problem-solving inventory scores and sub-scales indicate their problem-solving style (positive problem orientation, negative problem orientation, rational problem-solving, impulsivity/carelessness and avoidance⁶) and this allows the interventionist to customize the delivery of the intervention. During the first session, the interventionist works on steps one and two of the ADAPT model of the PST, namely “Attitude” and “Defining the Problem and Setting Realistic Goals.” For the first step the focus is on realistic optimism, i.e., acceptance that problems are a normal part of life. This step focuses on promoting visualizing successful problem solving, healthy thinking rules, positive self-talk and using emotions adaptively. The problems identified by the caregiver will be used as examples for exercises and to brainstorm about applying different approaches. The second step of defining the problem focuses on enabling caregivers to seek available facts, describe facts in a clear language, separate facts from assumptions, set realistic goals and identify obstacles to overcome.

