Demographic data: Standard demographic data were collected on patients and caregivers, including age, gender, nativity, education level, marital status, occupation, patient's diagnosis, relationship to patient, location of residence (residing with patient or not), estimate of average time spent on caregiving activities per week, impact on employment (whether caregiver had to decrease work hours or give up employment) and perceived income adequacy (having a comfortable income, having just enough to get by, not having enough to get by). Furthermore, if the patient dies during the subject's participation, that will be recorded along with the date of death (to allow for calculation of timing of death in the context of subject's days in the study).

Table 1 demonstrates the timeline for the collection of these measures.

Table 1: Timeline for data collection

	1 Baseline	2 Pre- Interventio n Assessme nt	3	4	5	6 Post-intervention Assessment	7 Exit interview
Group 1 PISCES delivered face to face Delivered by:	Demo- graphic data F2F I	Measures (PHQ-9, CQLI-R, PSI, GAD- 7) Telephone RA (blinded to group assignment)	PST Session 1 F2F I	PST Sessio n 2 F2F I	PST Session 3 F2F I	Measures (PHQ-9, CQLI-R, PSI, GAD-7) Telephone RA (blinded to group assignment)	Telephon e RA
Group 2 PISCES delivered in a hybrid format	Demo- graphic data F2F	Measures (PHQ-9, CQLI-R, PSI, GAD- 7) Telephone	PST Session 1 F2F	PST Sessio n 2 Video	PST Session 3 Video	Measures (PHQ-9, CQLI-R, PSI, GAD-7) Telephone	Exit interview Telephon e

Delivered by:	I	RA (blinded to group assignment)	I	I	I	RA (blinded to group assignment)	RA
Group 3 PISCESplus delivered in a hybrid format	Demo-graphic data	Measures (PHQ-9, CQLI-R, PSI, GAD-7)	PST+ positive reappraisal Session 1	PST+ positive reappraisal Session 2	PST+ positive reappraisal Session 3	Measures (Measures (PHQ-9, CQLI-R, PSI, GAD-7)	Exit interview Remove video
Delivered by:	I	RA (blinded to group assignment)	I	I	I	RA (blinded to group assignment)	Telephone RA
Group 4 PISCESplus delivered online	Demo-graphic data	Measures (PHQ-9, CQLI-R, PSI, GAD-7)	PST+ positive reappraisal Session 1	PST+ positive reappraisal Session 2	PST+ positive reappraisal Session 3	Measures (Measures (PHQ-9, CQLI-R, PSI, GAD-7)	Exit interview Remove video

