The primary analyses focused on examining differences between treatment groups in terms of caregiver outcomes during the time of intervention. Changes in caregivers’ scores from baseline to post-treatment will be analyzed using analysis of covariance, with baseline score, site, and whether the caregiver’s patient has died, as covariates. Separate models were run for each outcome (caregiver quality of life, anxiety, depression, and problem-solving ability). For Specific Aim 1 (SA1) to assess the equivalence between PISCES F2F and PISCES in hybrid format, a confidence interval approach was used on the ANCOVA model, with a two-sided 5% level of significance. If the CI of the difference between the two groups falls within the pre-specified range of equivalence, the two interventions will be considered equivalent.^{xiii xiv} The range of equivalence is defined between $-\Delta$ and $+\Delta$. The clinically informed Δ s for the primary outcomes are: CQLI-R = 1.0; GAD-7 = 1.75; PHQ-9 = 2.0; PSI = 2.5, respectively. The analyses of equivalence will be on a per-protocol basis and will be supplemented by secondary sensitivity intent-to-treat analyses.⁵⁵

The analyses for Specific Aim 2 (SA2) focus on pair-wise comparisons between PISCES*plus* and the other treatment groups. A significance level of $\alpha=0.025$ for each comparison was used to account for the multiple (2) comparisons and assure an overall significance level of no more than 0.05 for each outcome. These analyses of superiority was on an intent-to-treat basis, using

multiple imputation to address missing data. ANCOVA and chi-square tests were used to determine whether attrition had an impact on sample composition. Specifically, analyses were computed on baseline demographic characteristics, as well as baseline outcome measures, to determine whether participants who completed all phases of data collection were initially different when compared with persons who did not complete the intervention. Data were analyzed using the Stata statistical package.

Data Analysis for Specific Aim 3

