Our cost analysis compared the three intervention groups with respect to total costs. Using the resource use and cost information, and the cost of client-specific hospitalizations and emergency department visits as described earlier, we estimated the total cost of care for each client. These data were used as the dependent variable in four pair wise regression analyses comparing the four groups with respect to total costs incurred over the study timeframe. Analysis of variance methods was employed. We also examined resource use, and compared this between groups. Specifically, we compared the number of after-hours calls and, and the number of hospitalizations and emergency department visits. As these outcome variables are each an event-count, each cannot be truly normal in distribution. Traditional regression methods assume a normally distributed outcome with constant variance. In contrast, count data are discrete and usually involve many observations with identical values and often highly right-skewed due to a few individuals with extreme event counts. We used both Poisson regression and the Zero-Inflated Poisson model for a comparison of the number of after-hour visits and calls. We also controlled for demographic covariates in these models. Direct and indirect costs for the hospice program were computed as the sum of implementation and operating costs. Intervention implementation costs included equipment costs (based on equipment price and depreciation), and staff training costs. Operating costs were measured by staff costs (wages and time) for delivery of the intervention (based on average wages and average time research staff took to do the intervention), and costs of home visits (frequency and duration) by all hospice staff as documented in the record review. Caregiver costs were based on overall informal care time (using income data gather upon admission), intervention time, any time lost from work, and out-of-pocket and travel expenditures related to caregiving as reported by the caregiver during the exit interview.

Table 1: Participant characteristics

Variable	Traditional Pisces		Online Pisces		
	Group 1 (n = 154)	Group 2 (n = 152)	Group 3 (n = 154)	Online (n = 63)	P-value
Caregiver Age [Mean (Std.)]	56.8 (12.7)	58.8 (12.8)	57.4 (12.2)	56.1 (17.2)	0.5664
Caregiver GAD 7 Score [Mean (Std.)]	6.69 (5.4)	5.74 (4.9)	6.32 (4.9)	5.85 (5.2)	0.4236
Caregiver PHQ-9 Score [Mean (Std.)]	7.54 (5.7)	6.6 (5.4)	6.99 (5.3)	6.78 (5.36)	0.5267

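### Aim 4 compares raw event counts over an undefined period with no term for days at risk, so contrasts with Group 4, where bereavement is far lower, mix event rate with time observed

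*Combined protocol and SAP*

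**What the plan says.** The section Data Analysis for Specific Aim 4 gives two kinds of outcome.

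- **Cost.** The plan states that "we estimated the total cost of care for each client" and uses the result in pairwise regressions "comparing the four groups with respect to total costs incurred over the study timeframe". No start day, end day or length is given for that timeframe.
- **Resource use.** The plan compares after-hours calls and "the number of hospitalizations and emergency department visits". For the after-hours outcomes it says: "We used both Poisson regression and the Zero-Inflated Poisson model for a comparison of the number of after-hour visits and calls". The adjustment is: "We also controlled for demographic covariates in these models". No offset, person-time, death covariate or fixed window is mentioned.

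Three other places bear on this.

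- Under Measures, the demographic data paragraph covers a patient's death during the caregiver's participation: "that will be recorded along with the date of death". Its stated purpose is to place the death within the caregiver's days in the study.
- Data Analysis for Specific Aims 1 and 2 adjusts the caregiver outcomes for whether the "patient has died, as covariates". Aim 4 has no counterpart.
- The Group 1 description treats the session days as a guideline: "the actual timing and scheduling was tailored to the individual caregiver needs and challenges". The post-intervention assessment follows completion of the sessions, not a fixed day.

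**The concern.** After-hours calls, home visits, hospitalisations and emergency visits accrue mainly while the patient is alive and under observation. In hospice, death often ends that time early. A count model without an exposure term treats a client observed for a few days and one observed for the whole period as having had the same opportunity for events.

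This does little harm when time at risk is balanced across groups. Here the documents' own table suggests that it is not: the bereaved share in Group 4 is about a fifth of that in the other groups. A difference in after-hours calls between Group 4 and another group could then be read as an effect of fully online delivery when it reflects only more days alive. The zero-inflated model does not cure this. It allows for excess zeros, not for unequal time at risk.

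**Working it through.** **Step 1: the imbalance.** Inputs are the Caregiver Status rows of Table 1 (participant characteristics).

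| | Group 1 | Group 2 | Group 3 | Group 4 |
|---|---|---|---|---|
| Bereaved | 43 | 47 | 46 | 4 |
| Active | 107 | 102 | 103 | 59 |
| Total | 150 | 149 | 149 | 63 |
| Share bereaved | 0.287 | 0.315 | 0.309 | 0.063 |

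The Pearson chi-square on this 2 x 4 table is 16.35 on 3 df, p = 0.00096, which reproduces the printed 0.0010. Groups 1-3 alone give 0.32 on 2 df, p = 0.85. Group 4 (4/63) against Groups 1-3 pooled (136/448) gives 16.0 on 1 df, p = 0.00006. The imbalance is therefore Group 4 against the rest.

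**Step 2: does Aim 4 use Group 4?** The plan specifies four pairwise regressions among four groups without naming the pairs. Four groups make six pairs, and only three of them omit Group 4. If the four regressions are distinct, at least one includes Group 4.

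**Step 3: expected distortion of counts.** Assumptions, none of them given in the documents: a common window, the same daily event rate in every group, bereaved status standing for death within the window, and a bereaved client contributing on average a fraction f of the window.

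Mean exposure = 1 - (share bereaved) x (1 - f).

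For f = 0.5, Group 1 is 1 - 0.287 x 0.5 = 0.857, and Group 4 is 1 - 0.063 x 0.5 = 0.968. Their ratio is 0.968 / 0.857 = 1.13.

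| f | Exposure, Groups 1 / 2 / 3 / 4 | Group 4 ratio to Groups 1 / 2 / 3 |
|---|---|---|
| 0.75 | 0.928 / 0.921 / 0.923 / 0.984 | 1.06 / 1.07 / 1.07 |
| 0.5 | 0.857 / 0.842 / 0.846 / 0.968 | 1.13 / 1.15 / 1.14 |
| 0.25 | 0.785 / 0.763 / 0.768 / 0.952 | 1.21 / 1.25 / 1.24 |
| 0 (extreme) | 0.713 / 0.685 / 0.691 / 0.937 | 1.31 / 1.37 / 1.36 |

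The largest ratio within Groups 1-3, at f = 0, is 0.713 / 0.685 = 1.04. With a log-exposure offset the expected ratio is 1.00 throughout.

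**Step 4: effect on the test.** Poisson counts were simulated with no true rate difference, Group 4 (63) against Group 3 (149), using a two-sided 5% Wald test and 5,000 runs per setting. At f = 0.5, without an offset, the rejection rate was 10.6%, 15.4%, 24.9% and 41.5% for means of 0.5, 1, 2 and 4 events per full window. Over all settings with f of 0.25, 0.5 or 0.75, the offset brought it to 4.4%-5.5%. The event means are assumed.

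**Step 5: cost.** Let deaths fall halfway through, and let the last fifth of the window before death cost k times the usual daily amount. A bereaved client then costs 0.5 + 0.2 x (k - 1) of a full-window client. The Group 4 cost ratio is 1.13-1.15 at k = 1, 1.07-1.08 at k = 2, 1.02-1.03 at k = 3 and 0.98 at k = 4. It crosses 1 where 0.5 + 0.2 x (k - 1) = 1, that is, at k = 3.5. The documents give no daily costs, so k is unknown.

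**The case against.** Several objections have force.

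- **Direction for cost.** A reader might infer that groups with fewer deaths must look costlier. Step 5 shows that this needs roughly level spending up to death. The documents do not supply that, so the direction is open.
- **Total cost is a legitimate quantity.** Death ends spending; it is not missing follow-up. The plan's costs also include equipment, training and delivery of the sessions, which do not accrue by day. At the f = 0.5 exposures, dividing a fixed cost by days lived makes Group 4 look 12-13% cheaper by arithmetic alone (0.857 / 0.968 = 0.885; 0.842 / 0.968 = 0.870). A rule that accepts a total-cost difference only if it also appears per patient-day is therefore not justified.
- **Groups 1-3.** A reader might infer that flexible scheduling biases Group 1 against Group 2. All groups share the same suggested session days, no window lengths are reported, and nothing ties the cost window to session completion. This is a possibility only.
- **Timing of bereaved status.** The table does not say when it was measured. Eligibility requires the caregiver of an enrolled hospice patient, which favours death after entry but does not settle it.
- **False-positive rates.** They depend on the assumed means and on Poisson variance, whereas the plan itself expects right-skewed counts. With uniform death times, the rate is about 5% at 0.1 events and 7% at 0.2. With overdispersed counts and robust errors it is 8-13% at means of 1-3.
- **Case mix.** Group 4 also differs in dementia diagnosis (56.5% against 3.9-6.8%, on small denominators), in care-receiver gender (p = 0.0023) and in size. An offset does not make it comparable.

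None of these removes the need for an exposure term in the count models.

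**Conclusion.** The concern holds for the event counts in contrasts with Group 4. As written, those comparisons confound the event rate with patient-days at risk. The plan collects the date of death, which would help separate the two, but does not use it in Aim 4. The spurious Group 4 excess is about 6-7%, 13-15% or 21-25% for deaths three quarters, half or one quarter of the way through a common window. This is conditional on equal daily rates and on bereaved status marking death in that window. Among Groups 1-3 the effect of death is small, at most about 4% even at the extreme.

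For total cost, the documents support only the statement that totals combine daily cost with days observed. They do not support a direction. Confidence is medium. The change should be made, although Aim 4 lies outside the primary caregiver-outcome analyses.

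**What to change.** 1. Define the start and end of each client's observation period: for example, from enrolment to the earlier of patient death or a common end date, where the agency data allow it.
2. Include log(patient-days at risk) as an offset in every count model, using the recorded date of death. State which model applies to hospitalisations and emergency visits, since the Poisson and zero-inflated models are named only for after-hours visits and calls.
3. Keep total cost per client as the cost outcome. Beside it, report time-dependent service costs per patient-day as a sensitivity analysis, leaving out fixed equipment, training and session costs.
4. State when bereaved status was recorded, and interpret Group 4 contrasts with caution because its case mix also differs.

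**Cost.** No new assessment of caregivers is needed. The date of death and the hospice admission date are already among the planned data. The agency items under Measures for Specific Aim 4 do not list dates of individual services, however. If only totals were supplied, a common end date may not be applicable, and the days that those totals cover must be established first. Per-day rates give weight to the last days of life and condition on survival time, so raw counts and totals should stay alongside.

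### Aim 4's Poisson and zero-inflated Poisson models make no allowance for a few very high after-hours counts, so if such a tail is present group differences are declared too often

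*Combined protocol and SAP*

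**What the plan says.** Under Data Analysis for Specific Aim 4, the resource-use comparison is introduced with "we compared the number of after-hours calls and, and the number of hospitalizations and emergency department visits". Normal-theory regression is set aside for these outcomes: "As these outcome variables are each an event-count, each cannot be truly normal in distribution". The section then says that count data "usually involve many observations with identical values and often highly right-skewed due to a few individuals with extreme event counts".

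The models follow: "We used both Poisson regression and the Zero-Inflated Poisson model for a comparison of the number of after-hour visits and calls". On adjustment it adds: "We also controlled for demographic covariates in these models".

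Neither that section nor any other names a negative binomial model, a dispersion parameter, a robust or bootstrap variance, a dispersion check, or a rule for choosing between the two models. Hospitalizations and emergency department visits fall under the same rationale, but the model sentence covers only after-hours visits and calls. The software is named once, under Aims 1 and 2: "Data were analyzed using the Stata statistical package".

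**The concern.** The section gives two reasons why normal methods do not suit counts: many tied values, and a long right tail produced by a few people. If the ties are surplus zeros, ZIP answers the first reason. Nothing answers the second. A Poisson model sets the variance equal to the mean, and the count part of ZIP does the same for everyone outside its structural-zero class. If a few clients generate many calls, the true variance exceeds what either model allows. The model-based standard errors are then too small and the confidence intervals too narrow, and chance differences between delivery formats can be read as effects on resource use. Demographic covariates help only to the extent that they explain who the heavy users are.

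**Working it through.** The plan gives no Aim 4 figure to reproduce: no mean count, dispersion, level or power.

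**Inputs**
- Group sizes from Table 1 (Participant characteristics): 154, 152, 154 and 63. Simulations used 150 vs 150 and 63 vs 150.
- Level: two-sided 5%. This is an assumption for Aim 4, taken from the Aim 1 wording ("with a two-sided 5% level of significance").
- Mean count 1 or 2, and variance-to-mean ratio (VMR) 1 to 5. These are assumptions.

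**Formula.** With VMR = φ, the model-based Poisson variance of the log ratio is too small by the factor φ. The Wald statistic then has standard deviation √φ under no difference, so the true false-positive rate is 2(1 − Φ(1.96/√φ)). A correct interval is wider by √φ − 1.

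| VMR | 1.96/√φ | False positives | Widening needed |
|---|---|---|---|
| 1 | 1.960 | 5.0% | 0% |
| 1.5 | 1.600 | 11.0% | 22% |
| 2 | 1.386 | 16.6% | 41% |
| 3 | 1.132 | 25.8% | 73% |
| 5 | 0.877 | 38.1% | 124% |

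**Simulation, no true difference.** There were 20,000 replicates for Poisson and robust Poisson, and 3,000 for ZIP (constant inflation) and negative binomial. Three data types were used:
- Smooth tail: gamma-Poisson counts.
- Few extreme individuals: 95% of people at a low rate and 5% at a high rate. At mean 1 and VMR 2 the rates are 0.77 and 5.36. Check: mean 0.95 × 0.77 + 0.05 × 5.36 ≈ 1.00; variance of the rates 0.95 × 0.05 × 4.59² ≈ 1.00; VMR = 1 + 1.00/1.00 = 2.
- Excess zeros only: structural-zero share (VMR − 1)/(mean + VMR − 1), for example 50% at mean 1 and VMR 2.

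| Data type | Model | VMR 1.5 | VMR 2 | VMR 3 | VMR 5 |
|---|---|---|---|---|---|
| Smooth tail | Poisson | 11% | 16-17% | 25-26% | 37-38% |
| | ZIP | 7-9% | 11-13% | 18-20% | 29-32% |
| | Negative binomial | 4-6% | 4-6% | 4-6% | 4-6% |
| | Robust Poisson | 5-7% | 5-7% | 5-7% | 5-7% |
| Few extreme individuals | Poisson | 11% | 16-17% | 25-26% | 37-38% |
| | ZIP | 9-11% | 15-17% | 24-27% | 39-40% |
| | Negative binomial | 5-7% | 7-8% | 9-11% | 12-15% |
| | Robust Poisson | 5-8% | 5-8% | 5-8% | 5-8% |
| Excess zeros only | Poisson | 11% | 16-17% | 26% | not run |
| | ZIP | 5-6% | 5-6% | 5-6% | not run |
| | Negative binomial | 1-5% | 1-5% | 1-5% | not run |
| | Robust Poisson | 5% | 5% | 5% | not run |

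Where a row repeats one range, it is the range over all VMRs. At VMR 1 every model gave 4-6%. With few extreme individuals, robust Poisson gave 5-6% at 150 vs 150 and 6-8% at 63 vs 150.

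**Cross-checks**
- Smaller runs (500 replicates) with 5% of people at 8 times the rate (VMR about 2.7) gave Poisson 23.6%, ZIP 22.0% and robust Poisson 5.2% at 154 vs 152. At 154 vs 63 they gave 21.8%, 22.2% and 5.6%. Simulation error is about ±2 points near 5% and ±4 points near 30%.
- Letting ZIP's inflation part depend on group did not help: with extreme individuals, 19% at VMR 2 and 27-28% at VMR 3.
- If covariates carried half of the extra variance (assumption), adjusted Poisson still gave about 11%, 16% and 24-25% at VMR 2, 3 and 5.
- At means of 0.3-0.5, assumed for hospitalizations and emergency visits, VMR 1.5, 2 and 3 gave Poisson 10-11%, 16% and 24-26%. Robust Poisson gave 5-8%.

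**The case against.** The strongest reply is that no harm is documented. No Aim 4 count or result appears, since Tables 2 to 4 cover only GAD-7, PHQ-9 and caregiver quality of life. The remark about extreme counts concerns count data in general and does not forecast this trial's calls. The section is a short narrative, so a robust option may have been used and not described. No testing level is stated for Aim 4. These points stand. They are why the claim is conditional, and why overly narrow intervals are the firmer statement, with error rates as illustration. They do not remove the gap: the plan cites the tail as a reason to leave normal methods, then names two models that do not allow for it.

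ZIP does absorb part of a smooth tail, with 11-13% against 16-17% for Poisson at VMR 2. With a few extreme individuals it absorbs almost nothing. ZIP with covariates was not simulated.

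The remedy also has limits. The documents do not say how many clients had agency data. If coverage were as low as the diagnosis rows of Table 1, which sum to 51, 44, 45 and 23 (assumption), then at 23 vs 45-51 with few extreme individuals robust Poisson gives 7-8%, 9-10% and 12-14% at VMR 2, 3 and 5. That is above nominal but far below model-based Poisson. Zero-inflated negative binomial, bootstrap and permutation methods were not compared.

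**Conclusion.** The concern holds in its conditional form. As written, the two models understate uncertainty if the after-hours counts have the tail that the plan itself calls common. With a few extreme individuals at VMR 2 to 3, a nominal 5% comparison would be wrong about 15-27% of the time under either model. With a smooth tail, ZIP would be wrong 11-20% of the time. At VMR 1 there is no problem, and with surplus zeros alone ZIP is adequate. The size depends on assumed means, VMRs, group sizes and a 5% level. Only the Aim 4 resource-use comparison is affected, so this should be corrected but does not threaten the trial's main conclusions.

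**What to change.** - Make Poisson regression with robust standard errors the main model for after-hours visits and calls, and name it for hospitalizations and emergency department visits too.
- Report ratios of mean counts with 95% confidence intervals, the observed VMR, and the number of clients contributing counts in each group.
- Keep ZIP and negative binomial as sensitivity analyses. Negative binomial alone is not enough, since it reached 12-15% with few extreme individuals at VMR 5.
- For contrasts with the 63-person online group, note that the robust test can be slightly liberal (up to 8%), and more so if fewer clients have data.
- If a robust variance was in fact used, say so.

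The cost is small. No new data are needed, and the change is to the variance of a model already fitted. Against model-based Poisson, intervals widen by about 22%, 41%, 73% and 124% at VMR 1.5, 2, 3 and 5, and not at all at VMR 1. If the excess is only zeros, the change does not improve on ZIP's error rate.

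A separate, optional remark: no observation window is stated for the counts. Table 1 shows 4/63 bereaved in the online group against 136/448 in Groups 1-3 (43 + 47 + 46 of 150 + 149 + 149), with timing not given. A person-days offset could be shown beside the total counts for contrasts with that group.

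### Aim 4 compares after-hours visit and call counts with both a Poisson and a zero-inflated Poisson model, but names neither the deciding model nor the tested contrast, and states no robust variance

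*Combined protocol and SAP*

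**What the plan says.** The relevant text is in the combined protocol and SAP, under Data Analysis for Specific Aim 4. The aim is introduced with "We also examined resource use, and compared this between groups" and made specific as "Specifically, we compared the number of after-hours calls and, and the number of hospitalizations and emergency department visits". The section argues that ordinary regression does not suit event counts, which it describes as "often highly right-skewed due to a few individuals with extreme event counts". For after-hours use it then says "We used both Poisson regression and the Zero-Inflated Poisson model for a comparison of the number of after-hour visits and calls", and adds "We also controlled for demographic covariates in these models".

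On software, the analysis section for Aims 1 and 2 says "Data were analyzed using the Stata statistical package".

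The plan does not state:
- which of the two models decides if they disagree;
- which coefficient or contrast is the group comparison;
- whether group, or the covariates, enter the count part of the ZIP model, the inflation part or both;
- whether an overall mean ratio is derived from the ZIP fit;
- whether the Poisson standard errors are robust;
- a significance level for Aim 4.

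**The concern.** The question as worded is about the number of events, which most naturally means the mean count per client. A Poisson group coefficient addresses that directly. A ZIP model splits the same data in two: an inflation part for clients who would never call, and a count part for the rest. The count-part group coefficient compares rates among potential users. Any effect on who never calls goes into the other part.

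One question is therefore put to two models whose most visible group coefficients have different null hypotheses, with no rule for choosing between them. An analyst who reads the ZIP count coefficient as the answer may overlook a fall in calls that comes through more non-callers, or report a difference in number where the means are equal. An analyst who reads the Poisson coefficient has the right target, but with default standard errors that assume variance equal to the mean. The section's own description of the data makes that assumption doubtful.

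**Working it through.** **No figure to reproduce.** The documents give no sample size, power, zero share or call rate for this comparison.

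**Inputs from the documents.** Group sizes from the participant characteristics table: Group 1, 154; Group 2, 152; Group 4 (online), 63.

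**Assumptions.** Structural-zero share π, rate λ among potential users, two-sided 5%, no covariates, and data that follow a ZIP model exactly.

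**1. The two coefficients differ.** Under ZIP the overall mean is μ = (1 − π)λ. Hence

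log(μ₂/μ₁) = log(λ₂/λ₁) + log[(1 − π₂)/(1 − π₁)].

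Poisson regression targets the left side. The ZIP count coefficient is only the first term on the right. They agree only if π is the same in both groups. This is algebra and needs no assumed rates.

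**2. Default Poisson standard errors are too small.** Under ZIP, Var(Y) = μ(1 + πλ), while the default standard error assumes Var(Y) = μ. For identical groups the test statistic therefore has standard deviation √(1 + πλ) instead of 1. With λ = 2:
- π = 0.2: √1.4 = 1.18; 1.96/1.18 = 1.66; rejection about 10%.
- π = 0.4: √1.8 = 1.34; 1.96/1.34 = 1.46; rejection about 14% (simulated 13.5%).
- π = 0.5: √2 = 1.41; 1.96/1.41 = 1.39; rejection about 17% (simulated 17% to 18%).

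**3. Simulated rejection rates.** 154 v 152, 2,000 runs per row. The ZIP columns have group in both parts (count coefficient tested) or in the count part only.

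| Scenario (π, λ) | ZIP, both parts | ZIP, count part only | Poisson, default SE | Poisson, robust SE |
|---|---|---|---|---|
| Identical: (0.40, 2) in both | 4.5% | 4.6% | 13.5% | 4.0% |
| Real fall, mean ratio 0.83: π 0.40 to 0.50, λ 2 | 5.0% | 8% | 41% | 20% |
| Real fall, ratio 0.70: π 0.40 to 0.58, λ 2 | 4.2% | 16% | 81% | 59% |
| Real fall, ratio 0.60: π 0.40 to 0.64, λ 2 | 4.6% | 25% | 96% | 83% |
| Equal means 1.4: (0.30, 2) v (0.40, 2.33) | 27% | 16% | 14% | 5% |
| Equal means 1.4: (0.30, 2) v (0.50, 2.80) | 87% | 65% | 16% | 4% |
| Equal means 1.4: (0.30, 2) v (0.58, 3.33) | 99% | 96% | 19% | 5% |

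A second set has equal means of 1.0. For (0.50, 2) v (0.60, 2.5), the ZIP count coefficient with group in both parts rejected 37% to 39% of the time across separate runs. For (0.50, 2) v (0.667, 3) it rejected 86% to 87%. The robust mean test stayed between 4% and 6%.

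At 154 v 63 the pattern is the same. The ZIP count coefficient rejects 4% to 5% for the real falls and 18%, 63% and 92% in the three equal-mean rows. Default Poisson rejects 15% for identical groups.

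**The case against.** A reader might infer that the ZIP count coefficient is the plan's test, so that the plan would miss a real fall in calls. The documents do not support this. The same sentence names Poisson regression, whose coefficient targets the overall mean and rejects in 81% and 96% of runs for mean ratios of 0.70 and 0.60. Nor does the plan say which ZIP quantity is compared: group in both parts, a joint test or predicted means would all fit the text. That is an under-specification, not a stated wrong rule. This objection stands and sets the scope of the point.

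Two replies limit it. Part of the Poisson power is spurious, because the default test also rejects 13.5% of the time for identical groups. And a joint test of both ZIP parts would not settle the question: it has power 26%, 69% and 93% for the three falls, but rejects 32% to 100% of the time in the equal-mean rows.

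The scenarios are also open to challenge. Every arm receives PISCES or PISCES*plus*, and Groups 1 and 2 receive the same content in different formats, so a large shift in non-callers between those two has no support in the documents. The exact offset in the equal-mean rows is a construction. Both criticisms are fair, and the rates are illustrations. Equal zero shares cannot simply be taken for granted either. In the participant characteristics table 6.4% of the online group are bereaved, against 28.7% to 31.5% in the others. That bereavement affects who calls is an inference, not something the documents state.

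A reader might also infer that the cost comparison is compromised. It is not: total cost per client is the dependent variable in separate pairwise regressions that do not use the ZIP coefficient. Nor is any misreported result shown, since the results tables contain no count-model output.

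**Conclusion.** The concern holds as a gap in specification, and it is minor. One question is put to two models with different group coefficients, with no deciding model, no named contrast and no robust variance.

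- Reading the Poisson coefficient gives the right target with an inflated error rate: about 10% to 18% instead of 5%, for assumed zero shares of 20% to 50% at rate 2.
- Reading the ZIP count coefficient gives a different null: about 5% rejection for a fall that comes only through non-callers, and 39% to 86% rejection at equal means in the second set of assumed scenarios (27% to 99% in the table).

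The difference between the coefficients is certain. Its size is not, because it rests on assumed zero shares and rates and on a simulation without the plan's demographic covariates. The consequence is confined to the Aim 4 resource-use counts and does not touch the total-cost regressions or the Aim 1 and 2 caregiver outcomes.

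**What to change.** Replace the sentence that names the two models with text along these lines:

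> Groups are compared on the overall mean count per client. The deciding analysis is a log-link (Poisson) regression with robust standard errors, reported as a mean ratio with its confidence interval. A zero-inflated Poisson model is secondary, with group in both the count and the inflation part. Its group comparison is made on the model-predicted overall mean, and the two parts are reported only to describe how a difference arises.

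The cost is one sentence, a robust-variance option and one post-estimation command (Stata's margins after the ZIP fit), all on data already held. No new data are needed. The downside is some loss of power, compared with the ZIP count coefficient, when the effect lies only in the rate among users.
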